7.3 Bone marrow and blood diagnostics including central repository

The diagnosis of AML will be performed at the discretion of the participating centers, while material for the central repository has to be sent to one of the central laboratories of the SAL in Frankfurt, Dresden or Münster. Material for diagnostics may be sent to one of the three central laboratories of the SAL in Dresden, Frankfurt or Münster (address see 1). Reference diagnosis is a usual procedure in the management of AML.

Respective order forms can be downloaded from the German Leukemia Trial Registry at

http://www.kompetenznetz-leukaemie.de/content/aerzte/studien/studienregister/.

7.3.1 Cytomorphological examination and cytochemistry

Initial leukemia diagnostics and differentiation are based on the morphology of peripheral blood and bone marrow smears as well as on cytochemical examinations. If the bone marrow aspirate is not available, diagnosis will be based on the bone marrow biopsy or on peripheral blood. This should include a Pappenheim staining, a peroxidase reaction and an esterase reaction. Diagnosis and classification of the AML will be performed according to FAB criteria as well as according to the WHO classification. These analyses will be performed in the local participating centers.

The laboratories in Dresden, Frankfurt and Münster participate in round robin tests within the scope of the "network of excellence for acute and chronic leukemias" and offer reference laboratory diagnostics for discussion of questionable cases. To be able to quickly assess the diagnostic material, bone marrow and peripheral blood smears are requested for all patients at diagnosis (for shipping modalities, see 7.3). For discussion of cytomorphology, the laboratories in Dresden, Frankfurt or Münster can be contacted.

7.3.2 Immunophenotyping

An immunophenotyping of the leukemia cells should be performed for all patients. These analyses can be performed at the local study centers or at a laboratory of the investigators' choice. The immunophenotyping should be performed according to the proposals by the "network of excellence acute and chronic leukemias".

7.3.3 Cytogenetics

For each patient a cytogenetic examination should be performed at diagnosis. Chromosomal G-banding will be performed. Fluorescent-in-situ-hybridizations will be performed if

necessary. The cytogenetic examination will be performed by the local study centers or at a laboratory of the investigators' choice.

7.3.4 Molecular genetic analyses

All molecular genetic analyses may be performed at the participating centers or at a laboratory of the investigators' choice.

Molecular genetic analysis should include:

- determination of the presence or absence of BCR-ABL, PML-RARα, AML-ETO, and CBFβ-MYH11 fusion transcripts as determined by qualitative or quantitative RT-PCR
- Nucleophosmin 1 mutational status
- Determination of the presence or absence of Flt3-ITD and a quantification of the Flt3-ITD to Flt3-WT genomic ratio in case of the detection of Flt3-ITD

7.3.5 Central cell repositories and shipment modalities

For all patients diagnostic material should be send to one of the three central laboratories of the SAL for future scientific analysis:

10 ml bone marrow (Heparin)

20 ml peripheral blood (Heparin)

7.3.6 Requested material during treatment

Please refer to 7.2: Schedule of evaluations.

On day 1 after start of temsirolimus or placebo peripheral blood should be collected before the start of induction therapy for molecular biological analysis and sent to one of the three central laboratories of the SAL.

2 x 5 ml peripheral blood (Heparin)

Order forms can be downloaded from the German Leukemia Trial Registry at http://www.kompetenznetz-leukaemie.de/content/aerzte/studien/studienregister/.

All other follow-up tests in bone marrow or peripheral blood will be performed locally or at laboratories of the investigators' choice.

Order forms can be downloaded from the German Leukemia Trial Registry at http://www.kompetenznetz-leukaemie.de/content/aerzte/studien/studienregister/

Shipment is recommended from Monday through Thursday, if possible in the morning by express delivery or courier.

7.4 Duration of the study

Accrual time: 24 months F	Follow-up period ^a : 12 months
---------------------------	---

^a In case of a relapse / treatment failure, a study exclusion or a refusal of informed consent, the patients overall survival will be followed up until one year after the start of the first induction cycle.

Assuming an accrual time of 24 months and a duration of follow-up (of the last included patient) of approximately 12 months, the total duration of the study will be approximately 48 months.

7.5 End of study

The study will end one month after the end of the therapy, observation or follow-up period of the last patient.

7.6 Criteria for removal from study / premature end of study

7.6.1 Individual reasons (Criteria for removal of patients)

Patients will be removed from the trial for the following reasons:

- Drug-related toxicity
- Patient decision
- Incompliance
- Physician's decision

7.6.2 General reasons

The Coordinating Investigator, the BfArM and the EC have the right to terminate this clinical study at any time for reasonable medical or administrative reasons. Any possible premature

discontinuation would be documented adequately with reasons being stated, and information would have to be issued according to local requirements (e.g., IRB/EC, regulatory authorities, etc.). In terminating the Coordinating Investigator will assure that adequate consideration is given to the protection of the patients' interest.

8 ADVERSE EXPERIENCES

8.1 Introduction

An adverse event for the purposes of this protocol is the appearance of (or worsening of any pre-existing) undesirable signs, symptoms, or medical conditions occurring after signing the informed consent even if the event is not considered to be related to the study drug. Please refer to Section 6 for the protocol-specific definitions of study drug and study treatment. Adverse events (but not serious adverse events) occurring before starting study treatment but after signing the informed consent form are recorded on the Medical History/Current Medical Conditions Case Report Form. SAEs occurring after signing the Informed Consent are recorded on the Serious Adverse Event CRF. The occurrence of adverse events should be sought by non-directive questioning of the patient at each visit during the study. Adverse events also may be detected when they are volunteered by the patient during or between visits or through physical examination, laboratory test, or other assessments.

Where possible, a diagnosis rather than a list of symptoms should be given.

8.2 Severity of adverse events

Adverse events will be assessed according to the Common Toxicity Criteria for Adverse Events (CTCAE) version 4.0. If CTCAE grading does not exist for an adverse event, the severity of mild, moderate, severe, and life-threatening. CTCAE grade 5 (death) will not be used in this study; rather, this information will be collected in the End of Treatment or Survival Information CRF page. Adverse event monitoring should be continued for at least 30 days following the last dose of study treatment.

During the Run-in-Phase of the study, adverse events of all grades have to be documented in the Adverse Events CRF.

During the main part of the study, AEs grade 1 and grade 2 will be documented only in the patients file and AEs grade 3 and grade 4 will be documented in the Adverse Events CRF. (Since the majority of toxicities is expected from the underlying chemotherapy and is well known and documented in historic cohorts the documentation of adverse events will be restricted to grade 3-4.)

Symptoms of the disease under study should not be classified as AEs as long as they are within the normal day-to-day fluctuation or progression of the disease.

8.3 Adverse events associated with Laboratory Abnormalities

Abnormal laboratory values or test results constitute adverse events only if they induce clinical signs or symptoms, are considered clinically significant or require therapy (e.g., any hematologic abnormality that requires transfusion or cytokine treatment); and should be recorded on the Adverse Events CRF under the signs, symptoms or diagnosis associated with them. In addition, isolated abnormal laboratory values that are considered clinically significant (e.g., cause study discontinuation or constitutes in and of itself a Serious Adverse Event) should be recorded on the Adverse Events CRF.

8.4 Evaluation of adverse events

As far as possible, all adverse events which fulfill the above mentioned criteria for documentation in the CRF should be evaluated to determine:

- 1. The severity grade (mild, moderate, severe, life-threatening, fatal)
- 2. Its relationship to the study drug temsirolimus (related/unrelated)
- 3. Its duration (start and end dates or if continuing at final exam)
- 4. Action taken (no action taken; study drug dosage adjusted/temporarily interrupted; study drug permanently discontinued due to this adverse event; concomitant medication taken; non-drug therapy given; hospitalization/prolonged hospitalization)
- 5. Whether it is serious (see below)

8.5 Serious adverse events

A serious adverse event (SAE) is defined as an AE which:

- results in death
- is life-threatening (defined as an event in which the patient or patient was at risk of death at the time of the event; it does not refer to an event which hypothetically might have caused death if it were more severe),
- Results in persistent or significant disability/incapacity
- Constitutes a congenital anomaly/birth defect
- Results in the development of drug dependency or drug abuse
- Requires inpatient hospitalization or prolongation of existing hospitalization, unless hospitalization is for:

- Routine treatment or monitoring of the studied indication, not associated with any deterioration in condition (specify what this includes), including uncomplicated cytopenias
- Elective or pre-planned treatment for a pre-existing condition that is unrelated to the indication under study and has not worsened since signing the informed consent
- Treatment on an emergency outpatient basis for an event not fulfilling any of the definitions of a SAE given above and not resulting in hospital admission
- Social reasons and respite care in the absence of any deterioration in the patient's general condition
- Is medically significant, i.e., defined as an event that jeopardizes the patient or may require medical or surgical intervention to prevent one of the outcomes listed above
- Any other medical event considered serious by the treating physician

Any event including death that is clearly related to progression of leukemia is not regarded as SAE.

Unlike routine safety assessments, SAEs are monitored continuously and have special reporting requirements; see Section 8.7.

Careful medical judgment should be exercised to determine, if there is a causal relationship between an SAE and the investigational product. The following guidance is provided:

Certain:

- A clinical event, including laboratory test abnormality, occurring in a plausible time relationship to drug administration which cannot be explained by concurrent disease or other drugs or chemicals.
- The response to withdrawal of the drug (dechallenge) should be clinically plausible.
- The event must be pharmacologically or phenomenologically definitive, using a satisfactory rechallenge procedure, if necessary.

Probable:

- A clinical event, including laboratory test abnormality, with a reasonable time sequence to administration of the drug, unlikely to be attributed to concurrent disease or other drugs or chemicals.
- Clinically reasonable response on withdrawal (dechallenge).
- Rechallenge information is not required to fulfill this definition.

Possible:

- A clinical event, including laboratory test abnormality, with a reasonable time sequence to administration of the drug, which could also be explained by concurrent disease, or other drugs or chemicals.
- Information on drug withdrawal may be lacking or unclear.

Unlikely:

A clinical event, including laboratory test abnormality, with a temporal relationship
to drug administration in which a causal relationship appears to be improbable, and
in which other drugs, chemicals or underlying disease provide plausible
explanations.

Unrelated:

 A clinical event, including laboratory test abnormality, caused by other drugs, chemicals, underlying diseases.

In the complex medical situation of patients receiving an intense therapy with concomitant medications and the study drug, it will be difficult or impossible in many cases to assess "possible" relation to the study drug. Therefore, in case that the investigator assigns a "possible" correlation to the study drug the final decision on relation to the study drug and the prior description in the "Fachinformation" will be made during regular conferences of the DSMB.

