8.7 Serious adverse events reporting

If an adverse event is serious (see definition in section 8.5), additional reporting to the sponsor is required:

The investigator must inform the sponsor of any SAE within 24 hours of being aware of the event. Information not available at the time of initial reporting should be provided in a follow-up.

Any SAEs experienced within 30 days after end of study treatment should only be reported to the sponsor if the investigator suspects a causal relationship to the study drug.

Information about all SAEs is collected and recorded on the Serious Adverse Event Report Form. All Serious Adverse Event Reports sent to the sponsor must include the patient number, age, sex, weight, height, severity of reaction (Grade 1-5 according to CTCAE criteria), relationship to study drug (related, probably related, possibly related, probably unrelated, unrelated, not assessed), date and time of administration of study medications and all concomitant medications, and medical treatment provided. The investigator must assess and record the relationship of each SAE to the study drug temsirolimus (certain, probable, possible, unlikely, unrelated), complete the SAE Report Form in English, and send the completed, signed form immediately by fax to the Safety Desk.

The original copy of the SAE Report Form and the fax confirmation sheet must be kept with the case report form documentation at the study site.

Follow-up information which becomes available as the SAE evolves, as well as supporting documentation (e.g. hospital discharge summaries) should be collected subsequently, if not available at the time of the initial report. Follow-up information is immediately sent to the

sponsor, using a new SAE Report Form stating that this is a follow-up to the previously reported SAE and giving the date of the original report.

Re-occurrence, complication, or progression of the original event should be reported as a follow-up to that event regardless of when it occurs. The follow-up information should describe whether the event has resolved or continues, if and how it was treated, and whether the patient continued or withdrew from study participation. An SAE occurring at a different time interval or otherwise considered completely unrelated to a previously reported one should be reported separately as a new event.

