[contact]

For further information you may contact:

[contact]

It is the duty of the Safety Desk to inform the marketing authorization holder involved according to stipulation.

The initial SAE and follow-up SAE reports will be evaluated by the sponsor and if the SAE is not previously documented in the "Fachinformation" and is thought to be related to the study drug temsirolimus, the SAE Contact Center may urgently require further information from the investigator for Health Authority reporting. Suspected Unexpected Serious Adverse Reactions (SUSARs) will be collected and reported by the sponsor to the competent authorities and relevant ethics committees in accordance with Directive 2001/20/EC.

The Safety Desk will provide information for the Safety Data Monitoring Board as requested.

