8.8 Reporting of SUSARs

In case of the occurrence of a SUSAR it is the responsibility of the sponsor of the study to report these to the BfArM, the leading Ethics Committee, the Marketing Authorisation Holder as well as to the investigators of the trial – in line with the relevant national and European regulations. SUSARs will not be reported on national or international level to investigators of

other ongoing studies with the study drug and will not be reported to the IRBs of the participating centers.

The sponsor will inform relevant Regulatory Authorities and the Ethics Committee:

- of all relevant information about serious unexpected adverse events as
 defined above that are fatal or life threatening as soon as possible, and in
 any case no later than seven days after knowledge of such a case. Relevant
 follow-up information for these cases will subsequently be submitted within
 an additional eight days.
- of all other serious unexpected events suspected as defined above as soon as possible, but within a maximum of fifteen days of first knowledge by the investigator.

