11 QUALITY CONTROL AND QUALITY ASSURANCE

11.1 Data Safety Monitoring Board

The Data Safety Monitoring Board (DSMB) of this trial will consist of three members of the scientific community not involved in this trial. The committee will communicate regularly (by phone conference) with the Coordinating Investigator of the trial. The decision on the final dose for the main phase of the trial will be made in collaboration with the DSMB.

During the main part of the study, the DSMB will confer on a regular basis. The schedule and tasks of the DSMB will be written in a detailed DSMB charter. Notably, an interim analysis will be performed after 50 evaluable patients per treatment arm (temsirolimus vs. placebo) to determine the safety and the effectiveness (as measured by the % of patients with complete remission) of temsirolimus. In case the rate of complete remissions in patients of arm A (temsirolimus) is <50% of the remission rate in patients of arm B (placebo), the DSMB may opt to advise a discontinuation of the trial.

In case the DSMB has well founded reasons to suspect that risks of one treatment arm exceed the potential benefit, the DSMB has the right to request any information to be able to detect differences between the treatment arms. The DSMB will give recommendations about the continuation of the trial and/or about necessary trial amendments.

In the complex medical situation of patients receiving an intense therapy with concomitant medications and the study drug, it will be difficult or impossible in many cases to assess a "possible" relation to the study drug. Therefore, in case that the investigator assigns a "possible" correlation to the study drug the final decision on relation to the study drug and the prior description in the "Fachinformation" will be made during regular conferences of the DSMB.

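### The final relatedness and expectedness decision on SAEs rated possible goes to DSMB conferences of unstated frequency, and the protocol does not reconcile this with its 7- and 15-day SUSAR limits

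*Protocol*

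**What the plan says.** **The DSMB rule.** Section 8.5 defines five causality levels for SAEs: certain, probable, possible, unlikely and unrelated. It then singles out the possible level. When the investigator assigns it, the matter reserved for the DSMB is "the final decision on relation to the study drug and the prior description in the" Fachinformation, and this judgement "will be made during regular conferences of the DSMB". Section 11.1 repeats the rule. On timing, section 11.1 says only: "During the main part of the study, the DSMB will confer on a regular basis". It leaves the DSMB's schedule and tasks to a charter.

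**The investigator and the sponsor.** Section 8.7 makes the investigator responsible for the causality assessment of an SAE and requires a report to the sponsor within 24 hours. It then has the sponsor assess each SAE report, first or later. Where the event is not listed in the Fachinformation and a link to temsirolimus is suspected, more information may be sought urgently for reporting to the authority. The sponsor collects and reports SUSARs.

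**The limits.** Section 8.8 requires fatal or life-threatening unexpected events to reach the authorities and the ethics committee "no later than seven days after knowledge of such a case". Other serious unexpected events are due within 15 days of the investigator's first knowledge.

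**The scales.** One paragraph of section 8.7 asks for relationship on a list of six ("related, probably related, possibly related, probably unrelated, unrelated, not assessed") and, two sentences later, on the five levels of section 8.5.

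**The concern.** Whether an SAE is a SUSAR turns on two questions: is it suspected to be related, and is it already described in the reference document? For cases rated possible, the protocol gives both questions to three parties without ranking them in time. The party whose decision it calls final works to a conference calendar, while the limits in section 8.8 run from knowledge of the case.

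This is a stated rule that conflicts with other stated rules, so it is more than detail left to another document. At stake is whether a fatal or life-threatening unexpected event that the investigator thinks may be due to temsirolimus reaches the authority, the ethics committee and the other investigators in time. The possible level will not be rare. Sections 8.5 and 11.1 themselves expect attribution to be hard in many cases, because the patients receive intensive chemotherapy and other drugs alongside the study drug.

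**Working it through.** The protocol states no figure on this point, so there is none to reproduce. The check sets the sections side by side and then shows how far the outcome depends on the unstated interval.

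**Step 1. Who decides what, for an SAE rated possible**

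| Party | Section | Relatedness | Listing in the Fachinformation |
|---|---|---|---|
| Investigator | 8.7 | responsible for causality | not assigned |
| Sponsor | 8.7 | evaluates | evaluates |
| DSMB | 8.5, 11.1 | final decision | final decision |

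The sponsor and the DSMB hold the same two judgements. No section says whose view governs before the conference takes place.

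**Step 2. What the limits allow for**

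Section 8.8 gives 7 days from knowledge of the case and 15 days from the investigator's first knowledge. It contains no pause of the clock, no unscheduled DSMB call, and no statement that an undecided case counts as suspected in the meantime.

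**Step 3. Illustration by conference interval**

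Inputs:
- limits d = 7 and d = 15 days (section 8.8);
- conference interval T: not in the protocol, so a range is assumed;
- time of knowledge: assumed uniform over the interval between conferences;
- reporting: assumed to wait for the conference, which no section states.

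Share of cases whose next conference falls after the limit = max(0, 1 − d/T).

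| Assumed T | Past 7 days | Past 15 days |
|---|---|---|
| 7 days | 1 − 7/7 = 0% | 0% |
| 14 days | 1 − 7/14 = 50% | 0% |
| 30 days | 1 − 7/30 = 77% | 1 − 15/30 = 50% |
| 91 days | 1 − 7/91 = 92% | 1 − 15/91 = 84% |

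If one day is used up by the 24-hour report to the sponsor, d becomes 6 and 14. The 7-day column is then 14%, 57%, 80% and 93%, and the 15-day column 0%, 0%, 53% and 85%.

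So only conferences about once a week would nearly always fall inside the 7-day limit, and conferences about every two weeks inside the 15-day limit.

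**Step 4. The two scales in section 8.7**

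The six-level list has a level for causality not assessed; the five-level list does not. The remaining levels differ in name: related against certain, and probably unrelated against unlikely. Both lists contain a possible level, so the trigger for the DSMB rule can be identified on either. An SAE recorded as not assessed has no counterpart in section 8.5 and no stated route.

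**The case against.** **No section tells the sponsor to wait.** SAEs during treatment go to the sponsor within 24 hours, subject to the exceptions listed in section 8.7. The sponsor evaluates initial reports, and the 8.8 limits do not start from a DSMB decision. The DSMB's final decision can be read as later adjudication. This stands, and it rules out the reading that events rated possible are necessarily held back or missed. The protocol permits that outcome but does not prescribe it. The objection does not remove the conflict, because the text never says the decision is later adjudication, and a Safety Desk could follow it literally and report late.

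**The interval may be short.** Section 11.1 mentions contact by phone conference and leaves the schedule to a charter that is not shown. Weekly or unscheduled calls are not excluded. A reader might infer that the limits cannot be met; the documents support only that meeting them is not ensured. For the same reason, a figure such as 77% or 92% describes an assumed interval, not this trial. The result starts at 0% for weekly conferences.

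**Frequency.** A reader might infer that possible will be the commonest rating among drug-suspected events. The protocol gives no frequencies or ranking; it speaks only of many cases that are hard to judge.

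**The related/unrelated item in section 8.4.** It might be counted as a third conflicting scale that distorts toxicity by arm. It belongs to adverse event documentation in the CRF, and the toxicity endpoint in the synopsis is by CTC grade, not by attribution. I do not count it.

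**Conclusion.** The point holds as an unreconciled conflict among sections 8.5, 8.7, 8.8 and 11.1. The DSMB has the final word on relatedness and expectedness of SAEs rated possible, the investigator and the sponsor hold the same judgements elsewhere, and the reporting limits make no allowance for cases awaiting the DSMB. Timely expedited reporting of these cases is therefore not ensured.

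The size cannot be fixed from the documents. On the two assumptions that reporting waits for the DSMB and that conferences are evenly spaced, between 0% (weekly) and 92% (quarterly) of cases would pass the 7-day limit, and between 0% and 84% the 15-day limit. The double scale in section 8.7 is a smaller drafting fault; its practical effect is on SAEs recorded as not assessed.

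**What to change.** Reconcile sections 8.5, 8.7, 8.8 and 11.1 by stating that:

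1. SAEs the investigator rates certain, probable or possible are handled as suspected for expedited reporting.
2. The sponsor's Safety Desk determines expectedness against the Fachinformation and reports within the limits of section 8.8.
3. DSMB review of cases rated possible is later adjudication and neither delays nor replaces the report.
4. The SAE form uses the five-level scale of section 8.5, and the six-level list in section 8.7 is deleted.
5. An SAE whose causality is still missing is handled as suspected until it is rated.

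Item 5 is needed because the five-level scale has no level for causality not assessed. I do not propose limiting the direction in which the DSMB may change a rating, since nothing in the documents supports such a limit and items 1 to 3 protect the timing without it.

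The cost is a short amendment and a change to the causality field on the SAE form. The downside is some additional expedited reports for events later judged unrelated.
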